7.1 Methodology for obtaining and introducing UFCNPA, ^{99m}Tc

It is necessary to connect an argon gas cylinder to the TechnegasPlus generator and open the gas cylinder, connect the TechnegasPlus generator to the mains, turn on the TechnegasPlus generator and open the drawer. Remove the charcoal crucible from its packaging and place it on a watch glass. Before adding sodium pertechnetate, ^{99m}Tc ($\text{Na}^{99m}\text{TcO}_4$), it is necessary to moisten the crucible using absolute or 95% ethyl alcohol,

then the moistened crucible must be placed in the contacts of the drawer section. Next, the crucible must be filled with sodium pertechnetate, ^{99m}Tc ($\text{Na}^{99m}\text{TcO}_4$) with a volume of 0.1 to 0.3 ml with the required specific activity and close the drawer section. Start a slow heating cycle at the end of which, if necessary, you can refill the crucible with sodium pertechnetate, ^{99m}Tc ($\text{Na}^{99m}\text{TcO}_4$) to increase the specific activity, and repeat the slow heating cycle. Upon reaching the required specific activity, start the firing cycle, which consists in a short-term increase in temperature to 2700 ° C in an argon atmosphere, after which UFCNPA, ^{99m}Tc is ready for use within 10 minutes. After that, it is necessary to close the gas cylinder and disconnect it from the TechnegasPlus generator, turn off the TechnegasPlus generator and disconnect it from the mains.

For best results, ^{99m}Tc -labeled carbon ultrafine aerosol must be administered to the patient as soon as possible after being generated, and certainly within the 10 minutes allowed. The ^{99m}Tc -labeled carbon ultrafine aerosol is introduced to the patient through a series of deep and slow breaths with a 5 second delay of each breath through a special system of tubes and filters with a check valve. Before and during the inhalation of the ^{99m}Tc -labeled carbon ultrafine aerosol, all patients and volunteers will be tested for the degree of blood oxygen saturation (pulse oximetry).

7.2 Biodistribution UFCNPA, ^{99m}Tc

More than 96% of UFCNPA, ^{99m}Tc accumulates in the lung parenchyma within 6-48 hours after the end of inhalation. The bladder accumulates about 3-4% of the injected activity. The accumulation of the radiopharmaceutical in the parenchyma of the liver and spleen is not observed [13, 14].

7.3 Dosimetry

7.3.1. Measurements using a human phantom.

Measurements on a human phantom are carried out to obtain the coefficients of transition from the pulse count rate over the region of interest, obtained from planar scintigraphy in the "whole body" mode in the anterior and posterior direct projections (in imp./min), to the absolute activity of ^{99m}Tc in the region of interest (in kBq).

The measurements are made with the use of unified prefabricated human anthropometric phantoms UF-02T with different body manufactured by RADEK STC [15]. They are available at A. Tsyb MRRC.

Phantoms consist of rectangular polyethylene blocks weighing 1.0 kg and 0.5 kg. In the thoracic region of the phantom, there are phantoms of human lungs made of tissue-equivalent material with a density of 0.26 g / cm³ and a mass from 400 g to 1100 g, depending on the body weight of the phantom [16]. The phantoms of the lungs have through channels to accommodate sealed tubes with known ^{99m}Tc (kBq) activity, obtained from the ^{99m}Tc generator immediately before measurements. Measurements using planar scintigraphy with the following scanning parameters: low energy high resolution (LEHR) collimators, 140 keV photopeak (^{99m}Tc), discriminator window width $\pm 7.5\%$, tabletop speed 16 cm / min, matrix 256 \times 1024, are carried out and

recorded in strict compliance with the modes and geometry of measurements used in the corresponding measurements of patients and with the delineation of regions of interest.

According to the results of measurements on phantoms, the values of the transition coefficients from the counting rate of pulses in the region of interest (lungs) obtained from planar scintigraphy in the "whole body" mode in the anterior and posterior direct projections (in imp./min.) To the absolute activity of ^{99m}Tc in areas of interest (in kBq) - depending on the person's body weight. These coefficients are then used to determine the absolute activity of ^{99m}Tc in the lungs of patients with different body weights.

7.3.2 Determination of the accumulated absorbed dose in the lungs of volunteers under internal irradiation with ^{99m}Tc .

After inhalation of UFCNPA, ^{99m}Tc , each volunteer undergoes planar scintigraphy in the "whole body" mode in the anterior and posterior direct projections with contouring of the areas of interest (lungs, whole body, abdominal region) and recording the results of measurements over the regions of interest with the following scanning parameters: low collimators energy high resolution (LEHR), photopeak 140 keV (^{99m}Tc), discriminator window width $\pm 7.5\%$, table deck speed 16 cm / min, matrix 256×1024 . Measurements are carried out and recorded in strict accordance with the modes and geometry of measurements used in the corresponding measurements of phantoms. The body weight, height and age of the volunteer are recorded. The activity of the RFP for inhalation, loaded into the crucible of the TechnegasPlus generator, equal to 833 MBq, is recorded. The time interval between the preparation of the RFP for inhalation and the beginning of inhalation, as well as the duration of inhalation and the number of breaths / exhalations, are recorded. The number of impulses recorded over the areas of interest is recorded. Scintigraphy is performed at the following times after inhalation: 10 minutes, 1 hour, 3 hours, 6 hours, 8 hours, 24 hours. The exact time and duration are recorded. Based on the results of scintigraphy, the functions of retention and removal of the drug from the areas of interest are described. The values of the measurement results, expressed in pulses above the zones of interest, are converted into activity values, expressed in kBq, using the coefficients of the transition from the pulse count rate over the region of interest to the absolute activity of ^{99m}Tc in the region of interest obtained from the data of phantom measurements (see clause 7.3. one). The time integrals of these functions are the values of the accumulated activity (kBq \times h). The calculation of the accumulated absorbed doses in the lungs and organs of a volunteer from internal irradiation of ^{99m}Tc is carried out according to the methodology of the Medical Internal Dose Committee [17], taking into account the results of measurements of the accumulated activity of ^{99m}Tc and using databases containing the values of the specific absorbed energy fractions of quantum and corpuscular energy calculated by the Monte Carlo method radiation in organs and tissues of a person of different sex and age [18-33].

8. Selection and exclusion of patients participating in scientific research

8.1 Criteria for the inclusion of patients in the protocol:

1. The presence of a signed informed consent form (IC) for participation in the study (signed by the subject or his legal representative);

2. Men and non-pregnant women aged 18 years and older, at the time of signing the IP, with the presence of early laboratory signs of a cytokine storm in accordance with the interim guidelines for the prevention, diagnosis and treatment of new coronavirus infection (Covid-19): increased serum ferritin levels blood > 600 ng / ml or a combination of two of the following indicators: a decrease in the number of blood platelets $\leq 180 * 10^9 / l$, leukocytes $\leq 3.0 * 10^9 / l$, lymphopenia or a rapid decrease in the number of platelets and / or leukocytes (within 24 hours) more than doubled against the background of persistent high inflammatory activity, increased activity of AST, serum triglycerides > 156 mg / dL; decrease in blood fibrinogen (≤ 360 mg / dL) [30].

Men and non-pregnant women over the age of 65 years with or without the early laboratory signs of a cytokine storm indicated above.

3. A positive laboratory test result for the presence of SARS-CoV-2 RNA using nucleic acid amplification methods at the time of signing the IP;

4. Admission in a hospital with a radiographically confirmed diagnosis of pneumonia;

8.2 Exclusion criteria

1. Severe/ extremely severe course of COVID-19 illness, determined by the presence of any of the following signs:

- Acute respiratory failure with the need for invasive respiratory support (tracheal intubation);
- septic shock;
- Multiple organ failure;

2. Life forecast - less than 24 hours, according to the researcher;

3. Forecast of stay in the research center less than 48 hours;

4. The use of another non-standard therapy regimen for the treatment of COVID-19;

5. Established diagnosis of active tuberculosis;

6. Pregnancy or breastfeeding period;

7. Significant diseases or laboratory abnormalities that, in the opinion of the investigator, may increase the risks of participating in the study.

8.3 Criteria for excluding patients from research:

Research subjects will be excluded from further participation in the research in the following cases:

• Revealing, after inclusion of the subject in the study, gross violations of the inclusion / exclusion criteria;

• Withdrawal by the research subject of his consent to participate in the research (despite the fact that the subject has the right not to report the reasons for the withdrawal of the IP, the researcher should make every

possible effort to clarify the reasons for the subject's refusal to participate, for example: the subject does not have an effect from therapy; toxicity / intolerance, etc.);

- Loss to follow-up (this refers to repeated missed visits and inability to contact the subject in other ways. The investigator should make every possible effort to contact the subject and obtain more specific reasons for discontinuing participation, for example: the subject does not feel that the therapy is effective) ; toxicity / intolerance, etc.);

- Termination of the study as decided by local ethics committees or regulatory authorities.

9. Methods and terms of assessment, registration, accounting and analysis of performance indicators.

X-ray CT of the thoracic organs, detailed clinical and biochemical blood tests (ALT, AST, bilirubin, glucose, albumin, creatinine, LDH, CPK, troponin, lactate, ferritin, C-reactive protein, electrolytes), IL-6, NT-proBNP, coagulogram (APTT, prothrombin time, D-dimer), immunogram.

Terms: 1) the evaluation of the clinical results of treatment is carried out during the entire observation period for a limited period of hospitalization of the patient, on the 7th and 14th days after irradiation.

2) laboratory parameters assessment - during the in-patient period, in accordance with clinical need, but at least 4 times: before the start of RT, in 1, 3, 7 days after irradiation, and before the patient's discharge, cytokine levels - after 3 hours and after 10-12 hours from the procedure.

Table 2.

Methods of assessment	Terms
X-ray CT of thoracic organs	Before treatment, on 7 th and 14 th days after radionuclide therapy, or according to indications
Complete blood count (detailed)	- before treatment - on 1 st and 3 rd days after irradiation, then, according to indications, once every 2-3 days
ALT, AST, bilirubin, glucose, albumin, creatinine, LDH, lactate, electrolytes	- - before treatment - on the 1 st and 3 rd days after irradiation, then, according to indications, once every 2-3 days
CPK, troponin, C-reactive protein, IL-6, NT-proBNP, ferritin, procalcitonin	- before treatment - on the 1 st , 3 rd и 7 th days after treatment after irradiation, then, according to indications,
Coagulogram (APTT, prothrombin time, D-dimer)	- before treatment - on the 1 st , 3 rd и 7 th days after treatment after irradiation, then, according to indications,
Immunogram	- before treatment - on the 1 st , 3 rd и 7 th days after treatment after irradiation, then, according to indications,
Antibodies to SARS cov2 A, M, G	- before treatment - on the 7 th day after treatment after irradiation, then, according to indications,
Cytokine profile	before treatment, 3 hours after the procedure, 12 hours after the procedure, on the 3 rd and 7 th days after irradiation

10. Statistical Analysis Plan

Laboratory indicators were evaluated in accordance with the GLP criteria and with the laboratory standards for them. The assessment of biochemical parameters, the levels of circulating immune complexes and the antibody response to the SARS-cov2 pathogen was carried out on an automatic analyzer AU 480 (Becman Coulter). The hemostasis parameters were evaluated using an ALC Elit PRO automatic analyzer and a TAG 5000 thromboelastograph. The evaluation of immunological parameters was carried out in the direct immunofluorescence reaction with the detection of the results by 6-parameter flow cytometry on the FACS Canto II. Flow cytometry data were processed in the FCS3.0 and Kaluza software applications (Becman Coulter).

Statistical data processing was carried out using the SPSS 2020 program for Windows. The statistical analysis included an estimate of the average values for the sample size, the average value, the minimum and maximum values, the standard deviation, the sum, and the standard error of the average.

To determine the reliability of the differences in the indicators, a T-test for independent variables was used, where for each variable being compared, the sample size, the average value, the standard deviation and the standard error of the average value were compared. For the difference between the means: the average value, standard error, and confidence interval is assumed to be 95%, the significance of the differences is considered reliable at $p < 0.05$ and highly reliable at $p < 0.0001$. The Levin's criterion of equality of variances and the t-criterion of equality of averages for both the combined and separate variances are used.

11. References

4. Burch WM. Evidence for the long-term biological distribution of Technegas particles. *Nucl Med Commun.* 1993;14(7):559-561. doi:10.1097/00006231-199307000-00007.
5. <https://jcsmr.anu.edu.au/research/projects/technegas/clinical-issues-of-technegas-use>.
6. Sampson CB: Adverse reactions and drug interactions with radiopharmaceuticals. *Drug Saf* 8:280-294, 1993.
8. Gaurav Dhawan, Rachna Kapoor, Rajiv Dhawan, Ravinder Singh, Bharat Monga, James Giordano, and Edward J. Low dose radiation therapy as a potential life saving treatment for COVID-19-induced acute respiratory distress syndrome (ARDS). *Calabreseh Radiother Oncol.* 2020 Jun; 147: 212–216.

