To date, several pilot articles have been published in which the authors have demonstrated the feasibility and safety of low-dose irradiation in patients with COVID-19 associated with viral pneumonia [9, 10]. In the article "Low-Dose Whole-Lung Radiation for COVID-19 Pneumonia: Planned Day-7 Interim Analysis of a Registered Clinical Trial", the authors irradiated the entire lung volume with a dose of 1.5 Gy per 1 fraction in

five patients with various concomitant diseases, and the presence of severe respiratory distress requiring oxygen support. Within 24 hours after the session, 3 (60%) patients were removed from auxiliary methods of oxygenation, 4 people (80%) achieved CT-confirmed regression of pneumonia, no acute toxicity associated with radiation therapy was noted [9].

5. Goals and objectives of scientific research.

Objective: To determine the possibility, safety and effects of the use of inhaled low-dose radionuclide therapy in the complex treatment of patients with COVID-19 - associated viral pneumonia.

Tasks:

1. To investigate the dosimetric characteristics of the applied technique on anthropometric phantoms to obtain the coefficients of the transition from the rate of counting pulses over the region of interest to the activity contained in this region (in kBq).
2. To determine the accumulated dose in human lungs during internal irradiation of ^{99m}Tc in a group of healthy volunteers.
3. To develop a methodology for the use of inhaled low-dose radionuclide therapy in complex treatment of patients with COVID-19 - associated viral pneumonia.
4. To assess the possibility of using inhaled low-dose radionuclide therapy in the complex treatment of patients with COVID-19 - associated viral pneumonia.

6. Research design

At the first stage of preparation for the study, to obtain the coefficients of the transition from the pulse count rate over the region of interest to the absolute activity of ^{99m}Tc in the region of interest (in kBq), measurements will be made on a human phantom (see Section 7.3.1).

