At the second stage of preparation for the study to determine the accumulated absorbed dose in the lungs of a volunteer under internal irradiation of ^{99m}Tc after inhalation of UFCNPA, ^{99m}Tc obtained from the TechnegasPlus generator into the crucible of which an activity equal to 833MBq is loaded, a group of 5 volunteers without clinical and radiological signs of pneumonia will be preliminarily formed. For this purpose, at the initial stage, patients from this group will undergo: thermometry and physical examination, as well as X-ray CT of the thoracic organs. In addition, given the importance of immunological criteria in the pathogenesis of Covid-19, it is advisable to assess the immune status and the level of blood cytokines (pro-inflammatory cytokines: TNF α , IL-6, IL-12 TNF- α 4; anti-inflammatory cytokines IL-4, IL-10, TGF β).

In the absence of signs of pneumonia, patients in this group will undergo a single inhalation procedure, followed by a planar scintigraphy on a gamma camera at set intervals (see Item 7.3.2), and an assessment of the cytokine profile 3 hours after the procedure. The modes and geometry of measurements will strictly correspond to the modes and geometry of measurements on the phantom.

The study will enroll women and men aged 18 and over, hospitalized with a diagnosis of moderate new coronavirus infection (COVID-19) and receiving standard therapy.

Classification of COVID-19 by severity [11]:

Average, defined by the presence of at least one of the following signs:

- Fever above 38 ° C;
- NPV more than 22 / min;
- Shortness of breath during physical exertion;
- Pneumonia (susceptible to CT of the lungs);
- SpO2 <95%;
- CRP of blood serum more than 10 mg / l;

It is planned to include at least 10 patients in the protocol of a scientific prospective study.

All patients should undergo:

[figure not shown]
- laboratory test for confirmation of COVID-19 (PCR detection of SARS cov2 RNA);
- X-ray computed tomography of the thoracic organs, in which the presence of viral pneumonia is confirmed;
 - the levels of cytokines in blood plasma were determined (TNF α , IL-6, IL-12 TNF- α E, IL-4, IL-10, TGF β , interferon- γ -inducible protein (IP-10), monocyte chemoattractant protein 1 (MCP-1)
 - an assessment of the immune status was carried out,
 - biochemical indicators (levels of immunoglobulins and CEC) and indicators of the blood coagulation system (hemostasiogram) were evaluated;

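### CT is a scheduled effect measure, but no CT variable or masked reading is specified, and the only test named ignores that the scans come from the same patients

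*Combined protocol and SAP*

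**What the plan says.** Section 5 gives the objective as "To determine the possibility, safety and effects of the use of inhaled low-dose radionuclide therapy in the complex treatment of patients". It ranks no endpoint. Section 6 sets the size: "It is planned to include at least 10 patients in the protocol of a scientific prospective study". No concurrent patient control is described. The five volunteers have no pneumonia and serve the dosimetry.

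The list of performance indicators in Section 9 opens with "X-ray CT of the thoracic organs, detailed clinical and biochemical blood tests". Clinical results are evaluated "for a limited period of hospitalization of the patient, on the 7th and 14th days after irradiation". In Table 2 the row "X-ray CT of thoracic organs" gives the timing as "Before treatment, on 7 th and 14 th days after radionuclide therapy, or according to indications". It is the only row of that table with a fixed day-14 assessment.

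Section 10 describes how biochemical, haemostasis and immunological parameters are measured and does not mention CT. Its analyses are summary statistics (mean, range, SD, standard error) and one test: "To determine the reliability of the differences in the indicators, a T-test for independent variables was used". Significance is set at 0.05.

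**The concern.** There are three gaps, and each makes the others worse.

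- **No variable.** A mean or a t-test needs a number. At entry CT only has to confirm pneumonia, and no extent score, grade or response rule appears anywhere.
- **No protection from reader expectation.** Nothing says who reads the scans or whether the time point is hidden. In a before/after study, a reader who knows which scan followed treatment can tilt the reading towards regression.
- **A test that does not fit.** Baseline, day-7 and day-14 scans are repeated measures on one patient. A test for independent groups discards the pairing.

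The stake is how a reported CT improvement would be understood. Section 4 cites a five-patient pilot study in which 4 (80%) had regression on CT. A similar statement from this trial would invite the same reading, with neither a definition nor a safeguard behind it.

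**Working it through.** The plan gives no power, effect size, SD or CT success rate, so there is no figure to reproduce. The check shows how the stated test behaves on before/after data, and what a reader shift could do.

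**Inputs from the documents.** n = 10 (Section 6, the planned minimum); alpha = 0.05 (Section 10; two-sided assumed, as sidedness is not stated); t-test for independent variables (Section 10).

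**Assumed inputs.** Normal scores with equal SD σ at baseline and follow-up; correlation ρ between them of 0.3, 0.5 or 0.7; reader shift b of 0, 0.25 or 0.5 SD of the within-patient change. None of these values is in the documents.

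**Step 1: standard error.** For the same patients measured twice, the variance of the mean change is 2σ²(1−ρ)/n. The independent test uses 2σ²/n. Its standard error is therefore too large by a factor of 1/√(1−ρ):
- ρ = 0.3: 1/√0.7 = 1.20
- ρ = 0.5: 1/√0.5 = 1.41
- ρ = 0.7: 1/√0.3 = 1.83

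The pooled and separate-variance forms in Section 10 share this fault, since neither uses the pairing.

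**Step 2: paired test with a reader shift.** With no true change, t has 9 degrees of freedom, critical value 2.262 and noncentrality b√10:
- b = 0.25: 0.25 × 3.162 = 0.79, rejection 10.9%
- b = 0.5: 0.5 × 3.162 = 1.58, rejection 29.3%

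**Step 3: the stated test with the same shifts.** Within-patient change has SD σ√(2(1−ρ)), so a shift b adds bσ√(2(1−ρ)) to the follow-up score. The rejection rates below, with no true change, come from simulation for the independent test.

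| Reader shift b | Independent, ρ=0.3 | Independent, ρ=0.5 | Independent, ρ=0.7 | Paired |
|---|---|---|---|---|
| 0 | 2.3% | 0.9% | 0.2% | 5% |
| 0.25 | about 6% | about 3% | about 1% | 10.9% |
| 0.5 | about 21% | about 12% | about 4% | 29.3% |

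The first row concerns the test alone: it rejects far too rarely and would also miss real change. The other rows show that a shift raises the rejection rate well above the no-shift rate of whichever test is used, even where the stated test stays near or below 5%.

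**Step 4: workload.** 10 patients × 3 scheduled scans = 30 scans.

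**The case against.** The strongest reply is that the documents do not describe biased reading. They do not say who reads the scans, when, or with what knowledge. A reader might infer that scans are read unmasked as they arrive. The text supports only that masking is not specified. A reader might also take CT as the main endpoint because it heads the list, but no endpoint is ranked and none of the four tasks in Section 5 names CT. Both replies stand, and the point is limited accordingly.

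The second reply concerns size. The 11% and 29% figures belong to a paired test that the plan does not use. Under the stated test a 0.25 SD shift gives at most about 6%, and at ρ = 0.7 neither shift exceeds 5%. This also stands: the plan as written cannot be said to carry an 11% or 29% false-positive rate. But the stated test stays low only because its standard error is wrong, which is no safeguard. Nor does Section 10 say which comparisons the test is meant for. If it was meant for patients against volunteers, it would not serve CT either, since the volunteers are selected for having no pneumonia.

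The third reply is that no true change is an unrealistic null in patients on standard therapy, and that masked reading cannot cure the missing control. That is correct, and it limits what the fix can claim.

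**Conclusion.** The point holds in limited form. CT is a scheduled effect measure with no defined variable, no specified masking to time point, and no suitable analysis. The text of Sections 9 and 10 is intact here, so redaction does not explain the gap.

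The firmest numerical finding is the mismatch of the test: at n=10 and no true change it rejects 2.3% to 0.2% of the time instead of 5%, for assumed correlations of 0.3 to 0.7. The direction follows from any positive correlation; the size depends on its value. The reader-shift figures (about 21% to 4% under the stated test and 29% under a paired test, for 0.5 SD) are illustrations on an assumed shift. They are not estimates of what will happen in this trial.

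A reader might go further and expect masked scores to show whether the inhalation works. The design does not allow that: regression by day 7 or 14 can come from natural recovery or standard therapy, and the CT result should be reported as descriptive change. The amendment is worth making because it removes an avoidable bias and corrects a stated test at little cost.

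**What to change.** **Section 9.** Define one CT measure, for example percent of lung volume affected, for the scheduled baseline, day-7 and day-14 scans. A grade on a stated scale would also close the gap. Have a radiologist already on the study team score all these scans after the last one is taken, with dates removed and order shuffled. Clinical reads continue as usual.

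**Section 10.** For CT, replace the independent t-test with within-patient change from baseline to day 7 and to day 14, each with a 95% confidence interval. Report the number of patients with a scan at each time, because evaluation is tied to the hospital stay and day-14 scans may be missing. Do not substitute scans done on clinical indication for scheduled ones. State that the result is descriptive.

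**Cost.** One reading session of about 30 existing scans and a few lines of text; no extra scan or patient procedure. Use of existing staff is an assumption, since the documents do not name the reader. With about 10 patients, recall or visible disease stage may partly reveal the order, so masking reduces reader bias but may not remove it entirely.

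### The only test of means in the SAP is an independent-samples t-test, but the effect data are repeated measurements on one treated group, so its standard errors, intervals and p-values for before/after change are wrong

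*Combined protocol and SAP*

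**What the plan says.** Section 10 (Statistical Analysis Plan) lists descriptive statistics and then one test of means: "To determine the reliability of the differences in the indicators, a T-test for independent variables was used". It adds: "The Levin's criterion of equality of variances and the t-criterion of equality of averages for both the combined and separate variances are used". The significance level is 0.05 with a 95% confidence interval. The section does not say which indicators, groups or time points are compared. It names no paired t-test, signed-rank test, repeated-measures analysis or mixed model.

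Section 6 (Research design) sets the patient sample: "It is planned to include at least 10 patients in the protocol of a scientific prospective study". All of these patients receive the inhalation, and no control group or allocation is described. The only other people are 5 volunteers without pneumonia, studied for dosimetry at a loaded activity of 833 MBq; for patients the figure is 4165 MBq.

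Section 9 and its Table 2 schedule repeated measurements on the same patients:
- Laboratory parameters, as clinically needed, "but at least 4 times: before the start of RT, in 1, 3, 7 days after irradiation". The exact days differ by marker in Table 2.
- Cytokine profile: "before treatment, 3 hours after the procedure, 12 hours after the procedure, on the 3 rd and 7 th days after irradiation".
- Chest CT: "Before treatment, on 7 th and 14 th days after radionuclide therapy, or according to indications".

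**The concern.** With one group measured before and after, the informative quantity is each patient's own change. A two-sample t-test treats the two sets of values as coming from different people, so it leaves the covariance between a patient's two values out of the standard error. Laboratory values on the same person are usually positively correlated. In that case the standard error is too large, the interval is too wide and the p-value is too large.

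This is not harmless because it is conservative. Safety is part of the stated objective, and troponin, creatinine and D-dimer are followed before and after treatment. A test with inflated standard errors can miss a harmful rise as easily as a benefit. With about 10 patients, the pairing is the main source of precision that the design has.

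There is a second effect. Section 9 limits observation to the hospital stay, so some later samples may be missing. An unpaired test accepts different numbers before and after without warning, and would then compare different sets of patients.

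**Working it through.** The SAP gives no power, SD or effect size, and the figure of at least 10 patients has no derivation, so there is no stated result to reproduce. The check asks what the planned test does to paired data of this size.

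**Is the two-sample form really meant?** Yes. Levene's test and the choice between pooled and separate variances belong only to the two-group procedure. A paired test uses neither, so a translation slip for a paired test is unlikely.

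**Inputs**
- From the documents: n = 10 (Section 6); alpha 0.05 (Section 10), taken as two-sided because a 95% interval is specified.
- Assumed: equal SD before and after, normal data, and within-patient correlation rho over a range.

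**Formulas**
- Unpaired SE = SD × sqrt(2/n) = SD × sqrt(2/10) = 0.447 SD, with 18 df and critical t 2.101.
- Correct (paired) SE = SD × sqrt(2(1 − rho)/n), with 9 df and critical t 2.262. At rho = 0.5 this is SD × sqrt(0.1) = 0.316 SD.
- Ratio of the two = 1/sqrt(1 − rho). At rho = 0.5: 0.447/0.316 = 1.41.
- 95% half-width, unpaired: 2.101 × 0.447 = 0.94 SD. Paired at rho = 0.5: 2.262 × 0.316 = 0.72 SD.

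True size and power come from 200,000 simulated bivariate-normal trials per setting. Paired power agrees with the noncentral t.

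| rho | SE ratio | True size of nominal 5% test | Power for 1-SD change, unpaired | Power, paired | Half-width unpaired (SD) | Half-width paired (SD) |
|---|---|---|---|---|---|---|
| −0.3 | 0.88 | 8.2% | 56% | 42% | 0.94 | 1.15 |
| 0 | 1.00 | 5.0% | 56% | 51% | 0.94 | 1.01 |
| 0.1 | 1.05 | 4.0% | 56% | 55% | 0.94 | 0.96 |
| 0.2 | 1.12 | 3.1% | 57% | 61% | 0.94 | 0.90 |
| 0.3 | 1.20 | 2.2% | 57% | 66% | 0.94 | 0.85 |
| 0.5 | 1.41 | 0.9% | 59% | 80% | 0.94 | 0.72 |
| 0.7 | 1.83 | 0.2% | 61% | 95% | 0.94 | 0.55 |

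The unpaired standard error is right only at rho = 0. The paired test keeps its size at 5% throughout. For a smaller change of 0.8 SD, power is 38% unpaired against 48% paired at rho 0.3, 37% against 62% at 0.5, and 35% against 83% at 0.7.

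**Scale of measurement (secondary).** The SAP mentions no transformation. As an illustration only, take a log-normal marker with log-SD 1.0 and rho 0.6 that halves after treatment, n = 10. Power is 16% unpaired on raw values, 33% paired on raw values and 59% paired on logs. The first step is due to pairing, the second to the log scale.

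**The case against.** The strongest reply is that Section 10 never says it compares before with after. Independent groups can be found: patients against volunteers on cytokines at baseline and 3 hours, or patients with and without early cytokine-storm signs, since Section 8.1 admits those over 65 either way. It is true that the contrasts are not stated, and the error arises when the test is used for before/after change. But neither comparison is named, and neither answers the question about the effect of treatment. The volunteers have no pneumonia and a different loaded activity. If the test were reserved for such comparisons, the SAP would have no analysis of its main data, and the repair would be the same.

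Three further points stand as limits:
- With positive correlation the error costs precision and does not create false positives. Only negative correlation does that.
- rho is not in the documents. At 0 to 0.2 pairing gains little, and at 0 it loses about 5 points of power because it has 9 df where the unpaired test has 18.
- Skewness of the markers is an assumption, and analysing logs changes the estimand to a ratio of geometric means. The main point does not need it.

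It can also be said that the aim is broad, that no decision rule rests on a p-value, and that the data can be reanalysed later. That bears on urgency. It does not make the specified test suitable.

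**Conclusion.** The concern holds. The only test of means in the SAP assumes independent groups, while the study's effect data are repeated measurements on one group. At rho 0.3 to 0.7 the standard error is 20% to 83% too large. The nominal 5% test runs at about 2.2% down to 0.2%, and 9 to 34 percentage points of power are lost for a 1-SD change (66 − 57 and 95 − 61). These figures rest on n = 10, equal SDs, normality and an assumed rho. The mismatch between test and design does not depend on them. It should be corrected before analysis, because following the SAP as written gives wrong error bars for every before/after comparison unless rho happens to be zero.

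**What to change.** Rewrite the test paragraph of Section 10:

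1. Name the contrasts: for each marker, each scheduled post-treatment time in Table 2 against the pre-treatment value (for cytokines 3 h, 12 h, day 3 and day 7).
2. Replace the independent-samples t-test and Levene step for these contrasts with a within-patient analysis. Use a paired t-test, on log values for skewed markers, reporting the geometric mean ratio with its 95% interval and a Wilcoxon signed-rank test as a check. The alternative is one linear mixed model per marker with visit as fixed effect and patient as random effect. State in advance which is the main analysis.
3. State how missing later samples are handled, and report the number of patients contributing to each contrast.
4. Analyse the volunteers' baseline and 3-hour cytokines in the same paired way. Keep the Welch test only for a named comparison of different people.
5. State that, without a control group, a before/after change describes the course under combined treatment and is not by itself evidence of an effect of the inhalation.

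The cost is SAP wording only. The data, the visits and the software stay the same.
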